3.8.3 Exploratory Endpoints

- Descriptive statistics for concentration and change from baseline in IL-17, will be tabulated.

3.9 Safety Analysis

Safety assessments include AEs, serious adverse events (SAEs), vital sign measurements, clinical laboratory evaluations (hematology and chemistry), and ECGs. Unscheduled visits for safety assessments will not be presented in summary tables, but will be presented in listings. All safety analyses will be performed using the safety population.

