**Table 1-1 Schedule of Assessments**

Assessments	Screening	Double-Blind Treatment Period					32-Week Open-Label Continuation Period						Unscheduled or Early Termination b Visit (±3 days)	30-Day Follow-Up c (±3 days)
		Week 1	Week 4	Week 8	Week 12	Week 16 a	Week 20	Week 24	Week 30	Week 36	Week 42	Week 48		
Visit	1	2	3	4	5	6	7	8	9	10	11	12		
Day	-28 to -1	1 (Baseline)	28 (±3 days)	56 (±3 days)	84 (±3 days)	112 (±3 days)	140 (±3 days)	168 (±3 days)	210 (±3 days)	252 (±3 days)	294 (±3 days)	336 (±3 days)		
Informed consent	X													
Demographics and Medical history	X													
Physical examination d	X	X				X		X		X		X	X	X
Vital signs e	X	X	X	X	X	X	X	X	X	X	X	X	X	X
Hematology and serum chemistry f	X g	X	X	X	X	X	X	X	X	X	X	X	X	X
Lipid panel h	X g	X				X	X	X		X		X	X	X
PT, PTT, INR	X g	X				X	X	X		X		X	X	X
TSH	X g	X				X	X	X		X		X	X	X
Urinalysis	X g	X	X	X	X	X	X	X	X	X	X	X	X	X
Supine 12-Lead ECG i	X	X				X						X	X	
Pregnancy test j	X	X	X	X	X	X	X	X	X	X	X	X	X	X
Randomization k		X												
Photographs (optional) l		X				X						X	X	X
Punch Biopsy (optional) m		X				X								
PD whole blood sample n		X		X		X						X	X	X

Assessments	Screening	Double-Blind Treatment Period					32-Week Open-Label Continuation Period						Unscheduled or Early Termination b Visit (±3 days)	30-Day Follow-Up c (±3 days)
		Week 1	Week 4	Week 8	Week 12	Week 16 a	Week 20	Week 24	Week 30	Week 36	Week 42	Week 48		
Visit	1	2	3	4	5	6	7	8	9	10	11	12		
Day	-28 to -1	1 (Baseline)	28 (±3 days)	56 (±3 days)	84 (±3 days)	112 (±3 days)	140 (±3 days)	168 (±3 days)	210 (±3 days)	252 (±3 days)	294 (±3 days)	336 (±3 days)		
PASI Scoring	X e	X	X	X	X	X		X		X		X	X	
PGA Scoring		X	X	X	X	X		X		X		X	X	
DLQI	X	X	X	X	X	X		X		X		X	X	
Study drug administration p		X		X		X						X		
Dispense/Collect study drug Diary q		X				X						X	X	
Concomitant medications		To be collected from the date that the informed consent form is signed until 30 days after last dose of study drug.												
Adverse events														

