## 9.4 Evaluation of Liver-Related Blood Tests

Clinically significant elevations of liver-related blood tests as defined below require immediate drug termination.

1. ALT or AST  $> 5 \times$ ULN
2. ALT or AST  $> 3 \times$ ULN and (total bilirubin  $> 2 \times$ ULN or INR  $> 1.5$ )
3. ALT or AST  $> 3 \times$ ULN with the appearance of fatigue, nausea, vomiting, right upper quadrant pain or tenderness, fever, rash, and/or eosinophilia ( $> 5\%$ )
4. If the total bilirubin is  $> 2 \times$ ULN then obtain direct bilirubin

If ALT or AST  $> 2.0 \times$ ULN, the subject should remain on study drug with **close observation** which includes:

1. Repeating liver enzyme, every 48 to 72 hours  
(Frequency of retesting can decrease to once a week or less if abnormalities stabilize or the study drug has been discontinued and the subject is asymptomatic.)
2. Obtaining a more detailed history of symptoms and prior or concurrent diseases

3. Obtaining a history of concomitant drug use (including nonprescription medications and herbal and dietary supplement preparations), alcohol use, recreational drug use, and special diets
4. Ruling out acute viral hepatitis types A, B, and C
5. Obtaining a history of exposure to environmental chemical agents

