## 12.8 Safety Data

Safety assessments will include AEs, SAEs, PEs (including weight), vital sign measurements (including BP, pulse rate, respiratory rate, and temperature), clinical laboratory evaluations (hematology, chemistry, urinalysis, coagulation, lipid panel, TSH) ECGs, and reasons for treatment discontinuation due to toxicity.

The primary safety endpoint will be the percentage of subjects in each treatment group experiencing AEs.

TEAEs will be summarized by treatment group using MedDRA® SOC and preferred term, classified from verbatim terms (Version 18.1 or higher). The incidence and percentage of subjects with at least 1 occurrence of a preferred term will be included, according to the most

severe grade using a 5-point scale (mild, moderate, severe, life threatening, or death). The number of events per preferred term will also be summarized. Causality (relationship to study treatment) will be summarized separately.

AEs, SAEs, related AEs, related SAEs,  $\geq$  Grade 3 AEs, related  $\geq$  Grade 3 AEs, and AEs leading to withdrawal or treatment discontinuation will be summarized by treatment group according to SOC and preferred terms. AEs will also be presented in listings. Duration of AEs will be determined and included in listings, along with action taken and outcome.

Laboratory results will be classified using the Toxicity Grading Scale for Healthy Adult and Adolescent Volunteers Enrolled in Preventive Vaccine Clinical Studies (see Appendix A) and summarized. Incidence of laboratory abnormalities will be summarized by treatment group. The worst on-study grade after the first dose of study drug will be summarized by treatment group. The incidence of  $\geq$  Grade 3 laboratory abnormalities under treatment and shifts in toxicity grading from baseline to highest grade post-baseline will be displayed.

Vital sign measurements will be summarized at each scheduled time point using descriptive statistics.

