3.9.2 Clinical Laboratory Evaluation

The summary statistics (including number, mean, standard deviation, median, minimum and maximum) of all laboratory variables and changes from baseline will be calculated for each visit or study assessment by treatment group. For parameters of WCC, neutrophils (absolute count), lymphocytes (absolute count), monocytes (absolute count), Hb, platelets, ALP, ALT, AST, GGT, total bilirubin, GFR, plots of mean / mean changes from baseline with the corresponding standard error will be displayed.

For shift tables, laboratory results will be classified using the CTCAE V5.0. All graded laboratory parameters will be summarized separately for hematology and biochemistry. Corresponding shift tables to compare baseline to the worst post-baseline grade within the treatment period will be provided.

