3.14 Primary CSR Analysis

A primary CSR analysis will be conducted after conclusion of the study.

4 List of Tables, Figures and Listings

In all tables, figures and listing, results will be presented by treatment cohorts and overall, unless be otherwise specified.

Table 2: Demographics and Baseline Characteristics TLFs

T/F/L	Title	Population
T	Subject disposition	mITT
L	Subject disposition	mITT
L	Protocol deviations	mITT
T	Demographics and baseline characteristics	mITT
L	Demographics and baseline characteristics	mITT
T	Medical histories by primary system organ class and preferred terms	mITT
L	Medical history	mITT

Table 3: Efficacy TLFs

T/F/L	Title	Population
PASI		
T	The number (%) of subjects with a 75% decrease in PASI by Week 16	mITT
T	The number (%) of subjects with a 75% decrease in PASI by Week 48	mITT
T	PASI score, change and % change from baseline by visit	mITT
T	PASI change and % change from Week 16 to Week 48 visit	mITT
PGA		
T	The number (%) of subjects with “clear” and “almost clear” (excellent) in PGA at Week 16, 48	mITT
DLQI		

T/F/L	Title	Population
T	DLQI score, change and % change from baseline by visit	mITT
Exploratory Endpoints		
T	Descriptive statistics for IL-17 by visit	mITT

Table 4: Safety TLFs

T/F/L	Title	Population
T	Concomitant medications	mITT
L	Concomitant medications	mITT
T	Treatment exposure and compliance	mITT
L	Treatment exposure and compliance	mITT
T	Dose modifications and interruption	mITT
L	Dose modifications and interruption	mITT
T	Overall summary of TEAEs	Safety
T	TEAEs by Soc/PT	Safety
T	TEAEs by PT	Safety
T	TEAEs by severity and PT	Safety
T	Treatment related AEs by PT	Safety
T	Serious TEAEs by Soc/PT	Safety
T	Serious TEAEs by PT	Safety
T	Treatment related SAEs by PT	Safety
T	Grade 3-5 TEAEs by Soc/PT	Safety
T	Grade 3-5 TEAEs by PT	Safety
T	Treatment related grade 3-5 AEs by Soc/PT	Safety
L	AEs	Safety
L	AE Leading to treatment discontinuation	Safety
L	Death	Safety
T	Lab values and their change from baseline	Safety
F	Lab values by visit	Safety
T	Shifts in CTC grade from baseline to highest grade post-baseline of laboratory	Safety
L	Lab values with CTC grade ≥ 3	Safety

T	Vital signs and their change from baseline	Safety
L	Vital signs	Safety
T	ECG parameters and their change from baseline	Safety
F	ECG parameters by visit	Safety
T	Number and percentage of subjects with QTcF by visit a) absolute ranges and b) change from baseline	Safety
T	QTcF abnormalities	Safety
L	ECG values	Safety

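### SAP 3.9 keeps unscheduled visits out of safety summary tables without sparing the worst-grade lab shift tables, and the SAP grades on CTCAE V5.0 where the protocol specifies other scales

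*SAP*

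**What the plan says.** SAP 3.9 counts hematology and chemistry among the safety assessments and then sets a general rule: "Unscheduled visits for safety assessments will not be presented in summary tables, but will be presented in listings." No exception follows.

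SAP 3.9.2 describes the graded lab output: "Corresponding shift tables to compare baseline to the worst post-baseline grade within the treatment period will be provided." It does not say whether unscheduled values count. SAP Table 4 classes that output as a table, titled "Shifts in CTC grade from baseline to highest grade post-baseline of laboratory". Table 4 gives lab values of Grade 3 or higher only as a listing, so the shift table is the only lab table by grade that it names.

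Protocol 12.8 states: "The worst on-study grade after the first dose of study drug will be summarized by treatment group." It also asks for the incidence of Grade ≥3 lab abnormalities and for shifts to the highest post-baseline grade.

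For a subject with ALT or AST above 2.0 × ULN, Protocol 9.4 prescribes close observation, which includes "Repeating liver enzyme, every 48 to 72 hours". It allows a slower pace: "Frequency of retesting can decrease to once a week or less if abnormalities stabilize", or once the drug is stopped and the subject has no symptoms.

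On grading, SAP 3.9.2 says: "For shift tables, laboratory results will be classified using the CTCAE V5.0." SAP 3.9.1 names the same scale for AEs. The protocol uses Appendix E for AEs (11.1, 11.3.7), Table 9-2 for liver tests, and the vaccine-trial scale in Appendix A for other labs (7.2.4, 11.1, 11.3.10).

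**The concern.** The two SAP rules collide and the SAP does not say which one governs. A programmer who applies 3.9 literally will take the worst grade over scheduled visits only, which is not what Protocol 12.8 asks for.

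The error runs one way. The maximum over a subset of a subject's values cannot exceed the maximum over all of them, so the tabulated worst grade is either right or too low. Unscheduled liver values arise mainly because a liver test was already high. If KD025 raises transaminases, the active arms therefore lose more values than placebo, and the lab comparison between arms is flattened.

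This touches the known signal. Protocol 4.3 reports elevated ALT/AST, in about 20% of subjects, as the only adverse experience in the earlier dose-finding psoriasis study.

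The grading scale is a second, separate problem. Lab grades would be tabulated on a scale that the protocol does not specify, and the SAP gives no reason for the change.

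**Working it through.** The plan states no figure on this point, so there is none to reproduce. The check compares the texts, counts retests, and works one example.

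**1. Scheduled chemistry draws.** The "Hematology and serum chemistry" row of Protocol Table 1-1 gives on-treatment draws on Days 1, 28, 56, 84, 112, 140, 168, 210, 252, 294 and 336. The gaps are 27 to 28 days up to Week 24 (Day 168) and 42 days after it.

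**2. Retests strictly between two visits.** For a gap of *g* days and a retest every *s* days, count the multiples of *s* that are smaller than *g*. Visit windows are ignored.

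| Gap | Every 3 days | Every 2 days | Weekly |
|---|---|---|---|
| 28 days | 9 (Days 3 to 27 of the gap) | 28/2 − 1 = 13 | 28/7 − 1 = 3 |
| 42 days | 42/3 − 1 = 13 | 42/2 − 1 = 20 | 42/7 − 1 = 5 |

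The counts assume that the stated pace holds through the whole gap. Protocol 9.4 permits less than weekly, so a stable subject may have fewer than 3 or 5. Under a literal SAP 3.9, none of these results enters a summary table.

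**3. Worked example (hypothetical values, graded on Protocol Table 9-2).** For ALT, Grade 1 is 1.25–2.5 × ULN and Grade 2 is >2.5–5.0 × ULN.

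- Week 4, scheduled: 2.4 × ULN, Grade 1. This exceeds 2.0 × ULN, so retesting starts.
- Retest, unscheduled: 4.8 × ULN, Grade 2. Assume none of the symptoms or signs listed in 9.4 and no rise in bilirubin or INR.
- Week 8, scheduled: 1.8 × ULN, Grade 1.

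The worst of all values is Grade 2. The worst of scheduled values is Grade 1. The peak is below the >5 × ULN criterion, and the other termination criteria in 9.4 are not met, so no Early Termination draw would pick it up. It would also be absent from the Grade ≥3 listing.

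**4. Early Termination values.** Table 1-1 puts unscheduled and Early Termination visits in one column. The SAP does not say whether Early Termination labs count as unscheduled. It also sets no end to the treatment period for the shift table, so values just after the last dose are undefined as well.

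**5. Grading scales side by side.**

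| Data | SAP | Protocol |
|---|---|---|
| AE severity | CTCAE V5.0 (3.9.1) | Appendix E (11.1, 11.3.7) |
| Liver tests | CTCAE V5.0 (3.9.2; CTC in Table 4) | Table 9-2 (7.2.4, 11.1, 11.3.10, note in Appendix A) |
| Other labs | CTCAE V5.0 (3.9.2; CTC in Table 4) | Appendix A (7.2.4, 11.1, 11.3.10, 12.8) |

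For AEs the five severity labels are the same in both documents, so the SAP may only have misnamed the scale. For labs neither document gives CTCAE cut-offs, so the size and direction of any regrading cannot be computed from them. Protocol 12.8 cites Appendix A without repeating the liver exception, which Appendix A's own note makes.

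**The case against.** The best reply is that SAP 3.9 concerns the presentation of visits. It fits the by-visit descriptive tables, whereas a shift table shows no visits, and the more specific wording of 3.9.2 carries no limit to scheduled draws. The protocol also describes unscheduled visits as discretionary, while the liver retests are set out in Section 9.4, so they might not be unscheduled at all. That reading is reasonable, but the SAP nowhere states it, and Table 1-1 offers the retests no column other than the shared unscheduled/Early Termination one.

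Other points narrow the problem:

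- **AE reporting.** Lab abnormalities that change management, including added monitoring, are recorded as AEs (Protocol 7.2.4), so cases are not lost. But Appendix E grades on symptoms and function, and the note to Table 9-2 says that a lab grade does not imply the same TEAE grade. AE tables cannot stand in for lab-grade tables.
- **High peaks.** A value above 5 × ULN requires drug termination, and stopping study drug brings an Early Termination visit with chemistry. That draw may be below the peak, and its status in the SAP is unclear.
- **Listings.** A Grade ≥3 peak would appear in the listing, but a listing gives no count by arm.
- **Other graded output.** SAP 3.9.2 also mentions a general summary of graded labs. As a summary table it would meet the same exclusion.
- **Liver history.** The highest (Grade 3) elevations in the earlier study were at 400 mg BID, which is not used in this trial. This weakens the analogy but does not remove it.
- **Requested edits.** A shift table built on all values would already yield Grade ≥3 counts by arm, so the extra table is partly a matter of display. The Protocol 12.8 edit is housekeeping.

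Retest counts show how much data is exposed to the rule. They do not measure how often a worst grade is missed.

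**Conclusion.** The concern holds. As written, the SAP bars unscheduled values from every safety summary table and also promises a worst-grade table, with nothing to say which rule prevails. If 3.9 governs, the shift tables do not deliver what Protocol 12.8 requires and can only understate severity. The exposure is 9 to 13 liver results per 28-day gap and 13 to 20 per 42-day gap at the 48-to-72-hour pace, or 3 and 5 if weekly. The example shows a one-grade understatement. The number of subjects affected cannot be derived from the documents, and it is zero if the tables are programmed from all values.

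The scale mismatch is certain as a matter of text. Its effect on lab grades is undetermined, and for AEs it may be a label only. SAP 3.9.1 also mentions cGVHD, which is not the disease under study, so the CTCAE wording may be carried-over text. That is an inference. Both points should be corrected before the tables are programmed.

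**What to change.** - **SAP 3.9:** limit the exclusion of unscheduled visits to by-visit descriptive summaries. State that the worst-grade and shift tables, and the Grade ≥3 incidence required by Protocol 12.8, use all post-dose results, including unscheduled, repeat and Early Termination values. Define the end of the window.
- **SAP Table 4:** add a table of Grade ≥3 lab incidence by treatment group beside the existing listing.
- **SAP 3.9.1, 3.9.2 and Table 4:** name the protocol's scales (Appendix E for AEs, Table 9-2 for liver tests, Appendix A for other labs), with CTCAE only as an added, labelled display. Otherwise amend the protocol and justify the change.
- **Protocol 12.8:** state the Table 9-2 exception for liver tests.

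The cost is SAP wording, one worst-value derivation, one added table and a one-line protocol clarification. No new data are needed, and no clinical rule changes.

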3.9.1 Adverse Events

AEs will be coded using the Medical Dictionary for Regulatory Activities (MedDRA) dictionary (Version 20.0 or higher). TEAEs for blinded period and entire treatment duration are any AEs occurring or worsening in severity after the first administration of study medication. TEAEs for open-label period are any AEs occurring or worsening in severity after Week 16. All AEs (including SAEs) will be graded using the 5-point CTCAE V5.0 scale (mild, moderate, severe, life threatening, or death); their causality with KD025 will be classified into following 5 classes: definitely related, probably related, possibly related, unlikely related, not related. The Investigator will further assess the relationship of adverse events to cGVHD or the underlying disease.

The number and percentage of patients who experienced at least one TEAE as well as the number and percentage of patients who experienced adverse events of each specific system organ class (SOC) and preferred term (PT) will be presented. For the presentation of AE incidences, the SOCs and the PTs within each SOC will be presented by decreasing total frequency. Tabulation by maximum severity and relationship to KD025 will also be included by treatment group.

TEAEs, Grade ≥ 3 TEAEs, SAEs and TEAEs leading to dose modification / discontinuation will be summarized according to treatment arm, system-organ-class, and preferred terms. These analyses will be repeated for events considered related (definitely related / probably related / possibly related) to KD025.

Subject listings will be provided for SAEs, AEs resulting in study drug discontinuation and deaths.

AEs will also be presented in listings. Time to onset and duration of AEs will be included in listings, along with action taken and outcome.

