### **11.3.7 Recording Adverse Events**

All AEs (including SAEs) are to be accurately recorded on the Adverse Event page of the subject's eCRF during the subject's participation in the study. The severity of each AE will be graded using a 5-point scale (mild, moderate, severe, life threatening, or death; see Appendix E). The date of onset as well as the end date of the event also should be recorded or the event should be entered as "ongoing". In addition, the method used to treat the AE and the outcome of the AE also will be noted. The investigator will assess the relationship of the event to study drug.

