#### **11.3.10 Laboratory Data**

All laboratory data obtained during the course of the study should be reviewed. Any abnormal value that leads to a change in subject management (e.g., dose delay, requirement for additional medication or monitoring) or is considered to be of clinical significance by the investigator should be reported as an AE and/or SAE as appropriate, unless this value is consistent with the subject's present disease state or is consistent with values obtained prior to entry into the study.

With the exception of LFTs, laboratory results will be classified using the Toxicity Grading Scale for Healthy Adult and Adolescent Volunteers Enrolled in Preventive Vaccine Clinical Studies (see Appendix A). LFTs will be classified using Table 9-2 in Section 9.4.

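### The SAP names CTCAE V5.0 for AE grades and graded laboratory outputs, while the protocol prescribes Appendix E for AEs and Appendix A with Table 9-2 for laboratory results; the change is not declared

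*SAP*

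**What the plan says.** **Adverse events.** Protocol 11.3.7 sets the scale on which severity is entered on the eCRF: "The severity of each AE will be graded using a 5-point scale (mild, moderate, severe, life threatening, or death; see Appendix E". Protocol 11.1 names the same appendix for grading toxicities. SAP 3.9.1 says instead: "All AEs (including SAEs) will be graded using the 5-point CTCAE V5.0 scale". The same SAP section builds outputs on the grade: "TEAEs, Grade ≥ 3 TEAEs, SAEs and TEAEs leading to dose modification / discontinuation will be summarized". It repeats these for related events and adds a tabulation by maximum severity.

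**Laboratory results.** Protocol 7.2.4, 11.1 and 11.3.10 classify results by the vaccine-trial toxicity scale in Appendix A, with liver tests excepted. On those, 11.3.10 says: "LFTs will be classified using Table 9-2 in Section 9.4". Table 9-2 covers ALT, AST, alkaline phosphatase, GGT and bilirubin. For the analysis, protocol 12.8 says: "Laboratory results will be classified using the Toxicity Grading Scale for Healthy Adult and Adolescent Volunteers Enrolled in Preventive Vaccine Clinical Studies", with a pointer to Appendix A, and it promises Grade 3 or higher incidence and baseline-to-worst shifts. SAP 3.9.2 says: "For shift tables, laboratory results will be classified using the CTCAE V5.0". The output list in SAP Section 4 follows suit with "Shifts in CTC grade from baseline to highest grade post-baseline of laboratory" and "Lab values with CTC grade ≥ 3". It has no separate rule for liver tests.

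The SAP introduction says that the plan describes procedures as specified in protocol Amendment No. 2. It does not state or justify a change of grading scale. The protocol text does not mention CTCAE.

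**The concern.** A grade has meaning only together with the scale that defines it. AE severity is an investigator's judgement, made against a definition when the event is recorded. An SAP can choose how to tabulate that judgement, but it cannot change the definition the judgement was made against. A Grade 3 or higher AE table labelled CTCAE V5.0 would tell the reader that event-specific criteria had been applied, when the protocol called for one generic definition per grade.

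The laboratory problem is different. Grades are derived from reported values, so the choice of scale fixes the cut-points and hence the shift tables and the Grade 3 or higher listing. The protocol committed to one set of cut-points, including a dedicated liver scale, and the SAP uses another without saying so. Liver grades deserve care here. Protocol 4.3 reports ALT/AST elevations in about 20% of subjects in an earlier psoriasis study, with the highest (Grade 3) elevations in its 400 mg BID group.

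**Working it through.** The point depends on no power, alpha or event-count calculation. The check is a comparison of the texts, taken separately for AEs and laboratory values because the consequences differ.

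**1. Which scale does each document name?**

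| Item | Protocol | SAP |
|---|---|---|
| AE severity | Appendix E (11.1, 11.3.7) | CTCAE V5.0 (3.9.1) |
| Liver tests | Table 9-2 (7.2.4, 11.1, 11.3.10; Appendix A note) | CTCAE V5.0 (3.9.2, Section 4) |
| Other laboratory tests | Appendix A (7.2.4, 11.1, 11.3.10, 12.8) | CTCAE V5.0 (3.9.2, Section 4) |

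The named scale differs in all three rows.

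**2. Could AE grades be converted?** Appendix E has one functional definition per grade for every kind of event; Grade 3, for example, means that the subject is incapacitated and cannot carry on usual activities. SAP 3.9 describes no re-grading by medical review and no rule mapping Appendix E to CTCAE. Following the SAP therefore leaves two possibilities. Either the eCRF grades are tabulated as they stand under the name CTCAE, or they are re-graded by a method that is not specified. In the first case the counts are those recorded and the label is wrong. In the second the counts could change and the procedure is undefined.

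**3. Could laboratory grades be derived on either scale?** Yes. Under protocol 7.2.4 a central laboratory analyses the samples and results are classified afterwards. The same values can be graded by Appendix A and Table 9-2, or by CTCAE. What changes is the set of cut-points.

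**4. Which outputs are affected?** Going by the titles in SAP Section 4, Table 4:
- Four AE tables: TEAEs by severity, Grade 3–5 TEAEs in two layouts, and treatment-related Grade 3–5 AEs.
- Two laboratory outputs: the shift table and the Grade 3 or higher listing.

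That makes 4 + 2 = 6 outputs whose titles refer to severity or grade. The general AE listing may also show the grade.

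**5. Can the number of changed grades be worked out?** No. The protocol's cut-points are given (ALT or AST Grade 3 in Table 9-2 is above 5.0 and up to 10 × ULN), but the CTCAE V5.0 cut-points are not in either document. The protocol's own figures do show that a shift table depends on its scale. Inclusion criterion 7 admits haemoglobin above 9.0 g/dL, while Appendix A Grade 3 is 8.0–9.4 g/dL for women and 8.5–10.4 g/dL for men. A woman entering at 9.2 g/dL or a man at 10.0 g/dL is eligible and already Grade 3 at baseline on Appendix A.

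**The case against.** The best defence is that the AE discrepancy is probably only a label. The category names that the SAP puts in brackets after CTCAE V5.0 are those of Appendix E, and the same paragraph refers to chronic graft-versus-host disease, which is not under study. Both suggest text carried over from another plan. This stands as an explanation, and it is why the AE counts may not change. It does not remove the need to correct the scale name before it reaches the study report.

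A second defence is that protocol Section 12 leaves complete analysis details to the SAP. That would support a declared and justified change. It does not cover silent replacement of a named scale. Appendix A also has its own weakness for shift tables, as the haemoglobin example shows, so a sponsor might reasonably prefer another laboratory scale and could say so.

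A reader might infer more than the documents support:
- *That the laboratory data were collected on the wrong scale.* They were not collected on any scale; the values can be graded either way.
- *That protocol 12.8 drops the liver exception.* It points to Appendix A, which opens with a note sending liver tests and bilirubin to Table 9-2. Only the synopsis lacks both the exception and that pointer.
- *That about 18 subjects are affected, from 0.20 × 88 = 17.6.* That would project subjects with any ALT/AST elevation and not subjects whose grade would change. The 20% also comes from a 36-subject open-label study that included a 400 mg BID cohort not used here.
- *That Appendix A is stricter than CTCAE.* The documents give no CTCAE cut-points for comparison.

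**Conclusion.** The mismatch is explicit and should be corrected. For AEs, following the SAP puts a scale name on the Grade 3 or higher and maximum-severity tables that does not match how the protocol has severity recorded. This assumes that investigators graded as the protocol directs; the eCRF and its completion instructions are not among the documents. For laboratory results, the defect is an undeclared change of cut-points, including loss of the separate liver scale, in the shift table and the Grade 3 or higher listing.

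The size is moderate: six outputs by title, with an unknown number of laboratory grades changed and possibly no AE counts changed. SAP 3.9.2 still provides ungraded summaries of all laboratory variables, and mean plots for the liver tests. The liver termination criteria in protocol 9.4 use multiples of ULN with INR, symptoms or eosinophilia and do not use grades, so they do not depend on this point. The primary safety endpoint, the percentage of subjects with AEs, needs no grade, and the primary PASI 75 analysis is untouched.

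**What to change.** - **SAP 3.9.1:** replace CTCAE V5.0 with protocol Appendix E, as recorded on the eCRF.
- **SAP 3.9.2 and Section 4:** grade ALT, AST, alkaline phosphatase, GGT and bilirubin by Table 9-2 and other laboratory results by Appendix A. Rename the two CTC-grade outputs. Appendix A calls its values guidelines that depend on institutional norms, so the programming specification should say whether they are applied as printed.
- **If CTCAE laboratory grading is wanted:** declare it in the SAP as a change from the protocol, give the reason, and present it in a separately labelled table.
- **Optional tidying:** add the pointer to Appendix A and Table 9-2 to the laboratory paragraph of the protocol synopsis.

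The cost is minor SAP wording and programming work. No new data are needed.
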